The rationale for this study design is based on some of the feedback received from the VOICE and FEMPREP studies. Women in these studies reported high PrEP usage, remained in study and yet drug levels indicated very poor PrEP usage (Marazzo et al CROI 2013). Some rationale for this has been that PrEP acceptability was low, but with a keen perception among participants that study participation hinged on pill adherence. Thus, despite information that drug levels would be assessed, participants chose to report pill usage falsely. By making it very clear that trial participation does NOT hinge on PrEP usage (other than the first 3 months) we hope that we will get a more accurate assessment of real PrEP usage. We also hope that if participants really want to be taking PrEP, that adherence to product will persist. Other open label studies such as iPrEx OLE suggest this may be the case. By designing the study with an “opt out” arm we hope that we will create an authentic comparator group for participants taking oral PrEP (FTC/TDF) persistently and adherently, in order to assess any significant differences in adolescents taking oral PrEP (FTC/TDF) versus those who choose NOT to do so. We recognize that these may include demographic differences but may also include perceptions of risk, sexual activity, etc. In addition, we hope that this will give us a true sense of pill usage among this population- data that is currently unknown and required in order to more accurately model the impact of this intervention in this age group.

Both groups will be treated equally, except for administration of TDF/FTC therapy to those who select to include PrEP in their prevention package.

It was felt by the protocol team that the question of use and acceptability would best be answered by employing an open label design. The three month initial phase will mean that everyone will at least be exposed to 3 months of PrEP usage.

Adherence to medication can be measured in different ways depending on the condition and the

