4 STUDY DESIGN

4.1 IDENTIFICATION OF STUDY DESIGN

We propose an open-label phase II cohort study, to evaluate the acceptability, safety and use of, daily oral PrEP (FTC/TDF) in 150 HIV-negative adolescents at two sites (approximately 75 participants at each site), ages 15-19 years, as well as adherence to medication in participants who choose to have biofeedback of drug levels versus those who choose not to and any changes in their sexual and health behaviors over a 12-month (52 week) period. Enrolled participants will be stratified by gender (33% Male: 66% Female). Out of the 75 participants at each site, approximately 25 adolescent males and 50 adolescent females will be enrolled. This oversampling of women is to account for the fact that although oral PrEP is relevant to both genders, young women are more vulnerable to HIV acquisition in South Africa.

After a period of community engagement and general education about prevention packages including PrEP, participants will be invited to screen for this study. Those who are considered eligible will be asked to return for an enrollment visit. At enrollment, all participants who still wish to take part will be asked to take PrEP as part of a comprehensive prevention package for at least 3 months (12 weeks). During the first 3 months (12 weeks), participants will attend monthly (4 weekly) clinic visits for adherence counselling, trouble shooting, HIV testing and dried blood spot/plasma drug level sampling.

Researchers will use dried blood / plasma drug level sampling, combined with the reporting of results to individuals by the next visit, as an adherence enhancing strategy for those participants who elect to receive this information during adherence counselling at follow up visits. Those participants who agree to it, will receive blood drug level results during personal counseling in month 2 and 3 (weeks 8 and 12). Those who choose not to get this information will receive standard motivational adherence counseling during their study visits. Study staff will explore through standard questionnaires the reasons for not receiving drug level data.

Participants will be asked at the 3-month visit whether they would like to continue PrEP for a further 3 months. Those who opt out will continue to be followed in all aspects of the study except for distribution of Truvada pills. All participants will receive a brief questionnaire to explore reasons

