5.2 INCLUSION CRITERIA

Participants must meet all of the following criteria to be eligible for inclusion in the study:

1. Age 15 to 19 years (inclusive) at screening, verified per study site SOPs
2. Able and willing to provide written informed consent/ assent (age dependant) to be screened for and to take part in the study
3. Have a guardian who is able and willing to provide written informed consent for their child to be screened for and to take part in the study
4. Able and willing to provide adequate locator information, as defined in site SOPs
5. HIV-uninfected based on testing performed by study staff at screening and enrollment
6. Sexually active, as defined as a minimum of one act of (penile vaginal)sexual intercourse in the last 12 months, per self-report
7. (For female participants) Negative pregnancy test at screening and enrollment and per participant report, does not intend to become pregnant in the next 12 months
8. (For female participants) Using an effective method of contraception at enrolment, and intending to use an effective method for the study duration; effective methods include low dose oral, implant or injectable hormonal methods.
9. Does not report intention to relocate out of the study area during the course of the study
10. Does not have job or other obligations that would require long absences from the area (> 4 weeks at a time)
11. Willing to undergo all study-required procedures
12. At screening and enrollment, agrees not to participate in other research studies involving drugs or medical devices for the next 12 months

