CHAMPS: Choices For Adolescent Prevention Methods for SOUTH AFRICA

Pilot study B: “PlusPills”

A Demonstration Open Label Study to Assess the Acceptability and Use of Truvada Pre-exposure Prophylaxis in Healthy, HIV-Uninfected Adolescents, 15-19 Years of Age.

STATISTICAL ANALYSIS PLAN

OVERVIEW AND SUMMARY OF DESIGN

The study is designed as an open-label phase 2 demonstration project, to evaluate the acceptability, safety, feasibility, as well as the adherence to daily oral PrEP (FTC/TDF) for HIV-1 prevention, among 150 male and female adolescent participants at two sites (with approximately 75 participants at each site), ranging in ages between 15 and 19 years old, over a 12 month period. The study will also investigate the uptake and utility of feedback to the participants real time about drug levels obtained from dried blood spots/plasma during adherence counselling.

STUDY ENDPOINTS

Primary Acceptability/Use Endpoints:

Consistent with the primary study objective to evaluate the acceptability and use of daily oral PrEP (FTC/TDF) in HIV-negative adolescents, ages 15-19 years, the following primary safety endpoints will be assessed:

- The proportion of participants who report willingness to use the study regimen, take up PrEP and remain on PrEP as part of a comprehensive prevention package.
- An acceptability questionnaire will be administered at the final study visit to assess the delivery of PrEP and the content of the study visits, including the user-friendliness of the medication regimen (including an assessment of side effects), the delivery format, the dosing strategy, and the clinic visit schedule.
- Number of adolescents recruited, enrolled, and retained in the study.

Primary Safety Endpoint:

CHAMPS: Choices For Adolescent Prevention Methods for SOUTH AFRICA

Pilot study B: “PlusPills”

A Demonstration Open Label Study to Assess the Acceptability and Use of Truvada Pre-exposure Prophylaxis in Healthy, HIV-Uninfected Adolescents, 15-19 Years of Age.

- Grades 2, 3, and 4 clinical and laboratory adverse events;

Secondary Endpoints:

Consistent with the secondary study objectives to evaluate the adherence and sexual behaviour of daily oral PrEP (FTC/TDF) in HIV-negative adolescents, ages 15-19 years, the following endpoint will be assessed:

Adherence Endpoint:

- Adherence to daily regimens of oral PrEP as evidenced by self-report, pill counts, and proportion of participants assigned to FTC/TDF who have detectable drug levels.

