The DTHF protocol and research teams hypothesize that oral once daily PrEP (TDF/FTC) will be acceptable and utilized safely by healthy adolescents, between the ages of 15-19 years.

SAMPLE SIZE CONSIDERATIONS

The sample size calculation is based on the ability to detect the measure the primary

CHAMPS: Choices For Adolescent Prevention Methods for SOUTH AFRICA

Pilot study B: “PlusPills”

A Demonstration Open Label Study to Assess the Acceptability and Use of Truvada Pre-exposure Prophylaxis in Healthy, HIV-Uninfected Adolescents, 15-19 Years of Age.

objectives (acceptability and use) in the participant population. The table below shows the precision (as 95% confidence limits) provided by various sample sizes in detecting the occurrence of acceptability endpoints (with a frequency non- uptake and use varying from 5%-20%).

Acceptability will be measured by proportion of youth who take up PrEP and remain on PrEP as part of a comprehensive prevention package. Also they will complete an acceptability questionnaire.

	Precision *		
Frequency	n=100	n=135	n=170
5%	1.6; 11.2	2.1; 10.4	2.4; 9.8
10%	4.9; 17.6	5.7; 16.8	6.4; 16.2
15%	8.6; 23.5	9.9; 22.8	10.7; 22.2
20%	12.7; 29.1	14.2; 28.6	15.3; 28.1

* Asymptotic (exact) binomial 95% confidence limits

Based on these calculations, we anticipate that 135 participants, rounded up to 150 participants to account for premature censoring (due to loss to follow-up and/or withdrawal of consent, estimated at maximum 10%) will be required to detect non-acceptability endpoints that occur in 10% of subjects with approximately 5% precision.

DATA AND SAFETY MONITORING AND REVIEW

In addition to the informal safety monitoring done by the Site Investigator and study clinician, DTHF will convene an independent Protocol Safety Review Team (PSRT). The roles of the PSRT are:

CHAMPS: Choices For Adolescent Prevention Methods for SOUTH AFRICA

Pilot study B: “PlusPills”

A Demonstration Open Label Study to Assess the Acceptability and Use of Truvada Pre-exposure Prophylaxis in Healthy, HIV-Uninfected Adolescents, 15-19 Years of Age.

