participants. Should the SMC or the PSRT detect evidence of harm such that the recommendation for halting or modifying the study is made, then this will be communicated to the PI, The protocol team and the DAIDS prevention division. The IRB and MCC will also be informed of the discontinuation of the study and/or the modification and reasons for modification of the study. All further enrollment, and study activities other than safety follow up will be put on hold. Participants, guardians and CABS will be notified as soon as possible after next steps are identified.

DATA ANALYSIS PLAN

A customized data entry and management system will be implemented for the project in Microsoft Access. Data will be analysed using the statistical programme STATA (Stata Corporation, College Station, Texas, USA). Simple descriptive statistics including frequency distributions will be used to assist in data cleaning and summarization.

The analysis plan for each of the study objectives (per 10.2 above) is detailed below. (Note that throughout the analysis, all statistical tests will be 2-sided using an alpha of 0.05.)

Endpoints:

A. PRIMARY

1. Primary: Use

Number of adolescents who continue to use PrEP after the initial 3 month period and the total time on PrEP for each adolescent and for the cohort as a whole.

Analysis:

Proportions of participants (a) willing to use and (b) taking up PrEP will be described with point estimates and exact 95% confidence intervals. “Remaining on PrEP” will be defined as any self-reported use of PrEP at each study interval (regardless of adherence) over the 9-month follow-up period, as a binary outcome. The first 3-month “use” will be 100% for all 150 participants. We will use product-limit methods to examine ‘survival’ proportions for

CHAMPS: Choices For Adolescent Prevention Methods for SOUTH AFRICA

Pilot study B: “PlusPills”

A Demonstration Open Label Study to Assess the Acceptability and Use of Truvada Pre-exposure Prophylaxis in Healthy, HIV-Uninfected Adolescents, 15-19 Years of Age.

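### Initial PrEP uptake among the 150 enrolled is about 100% by design, so its planned confidence interval and factor tests cannot estimate uptake

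*SAP*

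**What the plan says.** The first primary endpoint in SAP Study Endpoints joins three things: willingness to use the regimen, taking it up, and remaining on it. SAP A.1 (Primary: Use) then treats the first two separately: "Proportions of participants (a) willing to use and (b) taking up PrEP will be described with point estimates and exact 95% confidence intervals". The denominator is participants, and no time point is given for either. The same paragraph adds "The first 3-month “use” will be 100% for all 150 participants". A.1 goes on to plan tests of factors associated with willingness, uptake and remaining on PrEP. Protocol 10.6 carries the same text.

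On entry, protocol 2.5 tells participants that "trial participation does NOT hinge on PrEP usage (other than the first 3 months") and says the lead-in means everyone is exposed for 3 months. Protocol 4.1 says that at enrolment "all participants who still wish to take part will be asked to take PrEP", for at least 12 weeks. Inclusion criterion 11 in protocol 5.2 is "Willing to undergo all study-required procedures".

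SAP Sample Size Considerations gives a precision table "with a frequency non- uptake and use varying from 5%-20" per cent. SAP Study Endpoints also lists "Number of adolescents recruited, enrolled, and retained in the study", but does not link those counts to the uptake proportion.

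**The concern.** Protocol 2.6.7, under non-adherence, separates initial uptake, persistence and quality of adherence, and says the study will investigate all three. Persistence data therefore cannot stand in for uptake. Yet an adolescent who does not want to take pills for 3 months has little reason to enrol, and someone who does not enrol is outside the planned denominator. The people who carry the information on non-uptake are the ones left out.

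At stake is one named component of a primary endpoint. It would be published with a narrow exact interval near 100%, which describes the entry process rather than adolescents' response to an offer of PrEP.

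**Working it through.** **Inputs.** From SAP Sample Size Considerations: 135 evaluable, 150 enrolled, loss of at most 10%, the exact-limit table, and the 5% to 20% range. From SAP A.1: 150 of 150 for initial use. Neither document gives a count of adolescents approached, screened or refusing.

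**1. The plan's own figures.** 135/(1 − 0.10) = 150, as stated. Exact (Clopper-Pearson) limits for 14/135 are 5.79% to 16.79%, against 5.7; 16.8 in the table. For 10/100 they are 4.90% to 17.62%, against 4.9; 17.6. All twelve cells agree within 0.1 point when the count is a whole number at or slightly above n × p. The Wald limits at 10% and n = 135 are 4.94% to 15.06% and do not match. The table is therefore the exact method, the same as A.1 plans for uptake.

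**2. The same method applied to uptake.** When all n take up, the lower limit is 0.025^(1/n).
- n = 150: 0.025^(1/150) = 0.9757, so 97.6% to 100%.
- n = 135: 97.3% to 100%.
- A few non-starters change little: 149/150 gives 96.3% to 99.98%, and 147/150 gives 94.3% to 99.6%.

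The number who refused enrolment does not enter this formula.

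**3. Can 5% to 20% describe initial uptake?** The chance of no non-starter in 150 is (1 − p)^150:
- p = 5%: 0.95^150 = 0.00046
- p = 10%: 0.90^150 = 1.4 × 10⁻⁷
- p = 20%: 0.80^150 = 2.9 × 10⁻¹⁵

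If the SAP's 100% statement stands, the range can only refer to later non-use.

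**4. What a wider denominator could show.** The denominators below are assumptions: the number of eligible adolescents offered enrolment, with 150 starting.

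| Offered (assumed) | Uptake | Exact 95% limits |
|---|---|---|
| 165 | 90.9% | 85.5 to 94.8 |
| 200 | 75.0% | 68.4 to 80.8 |
| 250 | 60.0% | 53.6 to 66.1 |
| 300 | 50.0% | 44.2 to 55.8 |

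In every row A.1 would report 100% (97.6 to 100).

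**5. Factor tests.** With no non-starters, a cross-table of uptake by any characteristic has an empty row. Neither a chi-square nor an exact test can then compare anything.

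**6. Willingness.** If recorded at entry, it is subject to the same selection. The protocol summary (Treatment Regimen) says that after 3 months tablets go only to those who indicate willingness, and protocol 7.4 repeats the choice at weeks 12, 24 and 36. On that reading willingness can vary, but it mostly duplicates remaining on PrEP. The two can differ where a willing participant has a clinical reason not to be supplied.

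**The case against.** The best defence is that the plan never dates willingness or uptake. The A.1 heading concerns use after the first 3 months, and the schedule of visits marks supply from week 12 as limited to the willing. Read that way, willingness is not fixed by design. This stands for willingness. It does not rescue initial uptake, which A.1 itself sets at 100%.

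Second, no criterion in protocol 5.2 names willingness to take PrEP; criterion 11 speaks of procedures. Participants are asked, and protocol 4.3 lets them opt out at any time. A reader might infer that agreeing to PrEP is a formal entry criterion. The documents do not say so. Selection follows from the lead-in described in 2.5 and 4.1, so about 100% is the right wording.

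Third, a reader might infer that the sample-size range contradicts the design. It does not have to: the phrase covers non-use as well as non-uptake, and the next paragraph of that section defines acceptability by taking up and remaining on PrEP. The range fits later discontinuation.

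Fourth, exposing everyone for 3 months is a declared choice, and the SAP states the 100% openly, so misreading is a risk rather than a certainty.

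Fifth, a denominator of all otherwise eligible adolescents offered the study cannot be obtained. Consent to screening and enrolment precedes every eligibility test (protocol 7.1 and 13.4), and recruitment runs through schools, taxi ranks and social media (5.4). This stands, and it limits the repair.

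**Conclusion.** The point holds for initial uptake. Among the 150 it is about 100% by design, its interval of 97.6% to 100% does not estimate uptake, and the uptake-factor tests have nothing to compare. Willingness has the same defect only if it is taken at entry.

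A reader might go further and infer that the trial cannot measure acceptability. The documents do not support that. The joint endpoint can fall as far as continuation falls. Product-limit curves for remaining on PrEP, time on PrEP, and the 3-monthly and final questionnaires can all vary.

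The conclusion rests on the SAP's own 100% statement and on the lead-in selecting adolescents who agree to it. The true gap between 100% and uptake among eligible adolescents is unknown; the figures in step 4 are illustrations, not estimates.

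**What to change.** In SAP A.1 and protocol 10.6:

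1. Define (a) as stated willingness at the choice visits in protocol 7.4 (weeks 12, 24 and 36). The design row of the protocol summary also lists week 48, and the two lists must be reconciled.
2. Do not report (b) among the 150 as an acceptability estimate. Report the number starting PrEP at Day 0 over those screened and found eligible. Alongside it, give a separate count of adolescents who declined before screening, with the reason (PrEP or other) where offered. The recruited and enrolled counts already listed as an endpoint supply most of this.
3. Make continuation after week 12 the proportion to which the precision table applies, and drop the tests of uptake factors among the enrolled.
4. State that conclusions on continued use apply to adolescents who agreed to start PrEP.

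The cost is revised wording and one reason-for-decline field. Data on refusals before screening will be incomplete, because eligibility is unknown there and a stated reason only partly separates PrEP from guardian consent, contraception or hepatitis B vaccination. The reported uptake is likely to look less favourable than 100%.
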